### 8.5.3 Pharmacokinetic parameters

The following PK parameters will be calculated with PKDMS software (Pharsight), using non-compartmental methods from plasma concentrations of isatuximab. The parameters will include, but may not be limited to the following:

**Table 5 - List of pharmacokinetic parameters and definitions**

Parameters	Isatuximab	Definition
$C_{\max}$	X	Maximum concentration observed after the first infusion
$t_{\max}$	X	Time to reach $C_{\max}$
$C_{\text{last}}$	X	Last concentration observed above the lower limit of quantification after the first infusion
$t_{\text{last}}$	X	Time of $C_{\text{last}}$
$C_{\text{trough}}$	X	Concentration observed just before treatment administration during repeated dosing
$AUC_{\text{last}}$	X	Area under the plasma concentration versus time curve calculated using the trapezoidal method from time zero to time of the last concentration observed above the lower limit of quantification (ie, $C_{\text{last}}$ )
$AUC_{0-T}$	X	Area under the plasma concentration versus time curve calculated using the trapezoidal method over the dosing interval T (336 h)

## 8.6 PHARMACODYNAMICS

### 8.6.1 Immunophenotyping

Levels of immune cells with high CD38 expression (ie, plasmablasts and NK cells) and low CD38 expression (B and T cells, including TREG cells) will be assessed by flow cytometry at the time points listed in the SoA ([Section 1.3](#)). Additionally, optional bone marrow biopsies/aspirates may allow for the assessment of plasma cells within the bone marrow. Details on processes for collection and shipment of these samples can be found in the laboratory manual.

## 8.7 GENETICS

Peripheral blood will be collected for DNA isolation on Day 1 for an analysis of immune genetic determinants to isatuximab response, such as Fc $\gamma$ RIII polymorphisms.

In the event of DNA extraction failure, a replacement genetic blood sample may be requested from the participant. Signed informed consent will be required to obtain a replacement sample unless it was included in the original consent.

See Appendix 5 ([Section 10.5](#)) for information regarding genetic research. Details on processes for collection and shipment and destruction of these samples can be found in the laboratory manual.

## 8.8 BIOMARKERS

Collection of samples for other biomarker research is also part of this study. Blood samples for biomarker research are required and will be collected from all participants in this study as specified in the SoA. Samples will be tested using RNAseq and/or single-cell RNAseq to evaluate the association of gene expression with the observed clinical response to isatuximab.

## 8.9 IMMUNOGENICITY ASSESSMENTS

Antibodies to isatuximab will be evaluated in plasma samples collected from all participants according to the SoA. Additionally, plasma samples should also be collected at the final visit from participants who discontinued study intervention or were withdrawn from the study. These samples will be tested by the Sponsor or Sponsor's designee.

Plasma samples will be screened for antibodies binding to isatuximab and the titer of confirmed positive samples will be reported. Other analyses may be performed to verify the stability of antibodies to isatuximab and/or further characterize the immunogenicity of isatuximab.

The detection and characterization of antibodies to isatuximab will be performed using a validated assay method by or under the supervision of the Sponsor. All samples collected for detection of antibodies to isatuximab will also be evaluated for isatuximab serum concentration to enable interpretation of the antibody data. Antibodies may be further characterized and/or evaluated for their ability to neutralize the activity of the study intervention(s). Samples may be stored for a

maximum of 5 years (or according to local regulations) following the last participant's last visit for the study at a facility selected by the Sponsor to enable further analysis of immune responses.

## **8.10 MEDICAL RESOURCE UTILIZATION AND HEALTH ECONOMICS**

Not applicable.

## **8.11 USE OF BIOLOGICAL SAMPLES AND DATA FOR FUTURE RESEARCH**

Future research may help further the understanding of disease subtypes, disease biology, related conditions, drug response and toxicity, and can help identify new drug targets or biomarkers that predict participant response to treatment. Therefore, data and biological samples will be stored and used for future research when consented to by participants unless prohibited by local laws or IRBs/IECs (in such case, consent for future use of sample will not be included in the local ICF).

For participants who consent to the storage and use of their data and remaining and/or extra clinical samples, data and samples may be used after the study ends for future research related either to the drug, the mechanism of action, and the disease or its associated conditions. Such research may include, but is not limited to, performing assessments on DNA, RNA, proteins or metabolites. If future research on genetic material is performed, this will also be limited to the purpose of addressing research questions related to the drug, the mechanism of action, the disease or its associated conditions.

In the event future research is conducted for other purposes, the study participants will be informed of those purposes and will be given means to object to those research projects. Data and samples will be used in compliance with the information provided to participants in the ICF Part 2 (future research).

All study participant data and samples will be coded such that no participant direct identifiers will be linked to them. Coded data and samples may be transferred to a Sponsor site (or a subcontractor site), which may be located outside of the country where the study is conducted. The Sponsor adopts safeguards for protecting participant confidentiality and personal data (see [Section 10.1.4](#)).

The samples will be stored for a maximum of 15 years after the end of the study. Any samples remaining at the end of retention period will be destroyed. If a participant requests destruction of his/her samples before the end of the retention period, the Investigator must notify the Sponsor (or its contract organization) in writing. In such case, samples will be destroyed and related coded data will be anonymized unless otherwise required by applicable laws.

Study participant coded data will be stored for future research for up to 25 years after the end of the study. If data are still considered of important scientific value after this period, coded data already available will be anonymized unless otherwise required by applicable laws (the same will apply to the data of a study participant who has requested the destruction of his/her samples). A participant's coded data sets provided to researchers for a specific research project will be available to the researchers for a maximum of 2 years after the end of their specific project (end of project is defined by publication of the results or finalization of the future research project report).

## 9 STATISTICAL CONSIDERATIONS

### 9.1 STATISTICAL HYPOTHESES

No formal statistical test will be performed.

### 9.2 SAMPLE SIZE DETERMINATION

#### 9.2.1 Part A

The primary objective of Part A is to evaluate the safety and tolerability of isatuximab in adults with wAIHA based on standard clinical and laboratory parameters and adverse events. A maximum of 9 participants will be assigned to the IMP in up to three successive cohorts. No sample size computation was done; sample size is based upon empirical considerations.

#### 9.2.2 Part B

The primary objective of Part B is to evaluate the efficacy of isatuximab in adults with wAIHA based on the Overall response rate (response (R) or complete response (CR)) at Day 85. Sample size calculations were performed to ensure reasonable accuracy for the estimation of the response rate. The maximal half-width (when a 50% response rate is observed) of the exact two-sided 95% confidence interval using Clopper-Pearson method is displayed for various sample sizes in [Table 6](#).

**Table 6 - Accuracy of the 95% confidence interval**

N	Response rate	Lower limit	Upper limit	Half-width
10	0.5	0.187	0.813	0.313
12	0.5	0.211	0.789	0.289
14	0.5	0.230	0.770	0.270
16	0.5	0.247	0.753	0.253

A sample size of 14 participants will provide a half-width for the 95% confidence interval of less than 0.275 which is deemed reasonable.

In addition to participants assigned to the IMP in Part B, the assessment of the proof of concept will include participants from Part A who received the same dose and number of administrations as selected for participants in Part B. Overall, approximately 14 participants assigned to the IMP at the selected dose will be included in the primary analysis, comprised of 0 to 6 participants from Part A and 8 to 14 participants from Part B.

### 9.3 POPULATIONS FOR ANALYSES

The populations for analyses are defined in [Table 7](#).

**Table 7 - Populations for analyses**

Population	Description
Screened	All participants who sign the ICF.
Efficacy	All participants exposed to the IMP (regardless of the amount of treatment administered).
Safety	All participants exposed to the IMP (regardless of the amount of treatment administered).
Pharmacokinetic	All participants exposed to the IMP (regardless of the amount of treatment administered), without any major or critical deviations related to IMP administration and for whom the PK data are considered sufficient and interpretable.
Pharmacodynamic	All participants exposed to the IMP (regardless of the amount of treatment administered), without any major or critical deviations impacting PD measurements, and for whom the PD data are considered sufficient and interpretable.
PK/PD population	All participants included in both the PK and the PD populations.

ICF: informed consent form, IMP: investigational medicinal product, PD: pharmacodynamic, PK: pharmacokinetic

### 9.4 STATISTICAL ANALYSES

The statistical analysis plan will be finalized prior to the database lock and it will include a more technical and detailed description of the statistical analyses described in this section. This section is a summary of the planned statistical analyses of the most important endpoints including primary and secondary endpoints.

The impact of a regional or national emergency declared by a governmental agency (see [Section 8](#)) on study conduct will be summarized (eg, study discontinuation or discontinuation, delay, or omission of the intervention due to the emergency). Any additional analyses and methods required to evaluate the impact on efficacy (eg, missing data due to the emergency) and safety will be detailed in the SAP.

#### 9.4.1 General considerations

Unless otherwise stated, all statistical analyses of Part B will include participants from Part A assigned to six administrations of the IMP at the selected dose for Part B, in addition to participants from Part B, and they will be described under Part B in what follows. All data from Part A will also be analyzed by dose level group separately.

Descriptive analyses will include summary statistics (using n, mean, standard deviation, inter quartile range, median, minimum, and maximum) for quantitative variables or number and percentage of participants in each category for qualitative data.

Participants from Cohort 1 in Part A may be retreated after Day 43 under specific conditions. If any, these participants will be followed for a total of 24 weeks from the first retreatment dose for safety, but the retreatment period will not be included in PK, PD, or efficacy analyses other than listings. Safety data post retreatment will be described or listed separately.

## 9.4.2 Primary endpoint(s)

### 9.4.2.1 Part A

**Table 8 - Primary endpoint analysis for Part A**

Primary endpoint	Statistical analysis methods
Standard clinical and laboratory parameters and adverse events.	Descriptive summaries of Treatment-Emergent Adverse Events and Potentially clinically significant abnormalities.

All the safety analyses will be performed using the safety population from Part A, by dose level group.

The safety evaluation will be based upon the review of the individual values (clinically significant abnormalities), descriptive statistics (summary tables, figures) and, if needed, on statistical analysis (appropriate estimations, confidence intervals).

Potentially clinically significant abnormality (PCSA) values are defined as abnormal values considered medically important by the Sponsor, according to predefined criteria/thresholds based on literature reviews and defined by the Sponsor for clinical laboratory tests and vital signs (from sponsor's document BTD-009536 "Analysis and reporting of safety data from Clinical Trials through the Clinical Study Report", Appendix 3).

Adverse events will be graded according to the NCI-CTCAE v5.0 and related analyses will be provided by grades. For clinical laboratory evaluation, vital signs, and physical examination, analyses will be provided according to PCSA.

For all safety data, the following observation periods are defined and used for classification of AEs and determination of on-treatment PCSA values:

- The **pre-treatment period** is defined as the time between informed consent signature and the first IMP administration.
- The **treatment emergent (TE) period** is defined as the period from the first IMP administration up to 30 days after the last IMP administration.
- The **post-treatment period** is defined as the time starting after the TE period.

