#### Pharmacokinetics

PK (isatuximab)	P00 j	P01	P02	P03	P04 j	P05 j	P06 j	P07 j	P08 j	P09	P10	P11	P12	AB02	AB03 m	X
Antidrug antibodies		AB00 j					AB01 j									

a Visits on Days 3, 5, and 8 may be performed with a home nursing service.

b Includes details regarding DAT positivity, anti-RBC antibodies (if known), and treatment history including current therapy.

c Includes at minimum an assessment of the skin, lungs, cardiovascular system, and abdomen, as well as weight and height (height only measured at screening). Physical exams may be performed on an ad hoc basis at other visits as per the discretion of the investigator based on the assessment of AEs.

d On Day 1, vital signs will be assessed prior to isatuximab administration and 1 hour, 2 hours, and 4 hours after administration. On Day 15, vital signs will be assessed prior to isatuximab administration and 1 hour after administration. On other days of isatuximab administration, vital signs will be assessed prior to isatuximab administration and 1 hour and 2 hours after administration. On other days of isatuximab administration, vital signs will be assessed prior to isatuximab administration and 1 hour after administration. On Day 15, vital signs will be assessed prior to isatuximab administration and 1 hour after administration.

e The first 3 participants in the study (Part A, Cohort 1) will receive the D1 and D15 doses only. Retreatment of these participants may occur as per [Section 6.6.1](#). In that case, participants will follow the SoA as above except for visits at Days 3 and 5. All safety assessments as well as complete blood count, LDH, haptoglobin, total bilirubin, reticulocytes, and ADA will be performed as per the SoA. The other efficacy, biomarker, and pharmacokinetic assessments will not be performed.

f Hepatitis B and C testing includes: HBsAg, anti-HBs, anti-HBC (total and IgM, followed by HBV DNA in case of anti-HBC positivity), anti-HCV Ab, and HCV RNA (if anti-HCV Ab is positive). Need for SARS-CoV-2 testing to be determined for each site, and should be a molecular test. If HBV vaccination will be started before the first study administration, anti-HBs should be monitored at 1, 2, and 3 months after the end of vaccination.

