## 4 STUDY DESIGN

### 4.1 OVERALL DESIGN

This is a Phase 1b/2 open-label, non-randomized, multicenter study to evaluate the safety, pharmacokinetics, and efficacy of subcutaneous isatuximab in adults with wAIHA. The study will be conducted in 2 parts: Part A for safety and dose-finding, and Part B for assessment of the efficacy of the selected dose regimen. Approximately 17 to 23 participants are expected to be enrolled, depending on the number of participants in Part A who receive the regimen chosen for Part B.

Part A will have 2 to 3 cohorts. Cohort 1 consists of 3 participants who will receive 2 doses of isatuximab 140 mg (1 mL) SC administered 2 weeks apart. Cohort 2 can open following a review of available safety, pharmacokinetic (PK), and pharmacodynamic (PD) data after the 3 participants in Cohort 1 complete the Day 43 visit. Cohort 2 will consist of 3 participants who will receive isatuximab SC given every 2 weeks through Day 71 (total of 6 doses). The dose for Cohort 2 may be 70 mg (0.5 mL), 140 mg (1 mL), or 280 mg (2 mL), determined based on the safety profile, PK, and PD observed in Cohort 1.

Once the 3 participants in Cohort 2 have completed the Day 85 visit, an analysis of the available safety, PK, and PD data will be performed, and a decision will be made to either enroll 3 participants as an additional optional dose-finding cohort (Cohort 3) in which a dose up to 560 mg (4 mL) can be investigated, or to open Part B. If Cohort 3 is enrolled, Part B will open once available safety, PK, and PD data through the Day 85 visit from those participants have been reviewed.

Participants in Cohort 1 who experience no response by the end of the treatment period, or a response that subsequently wanes while still in follow up, can be retreated, after completing the Day 43 visit, with 6 administrations of the dose selected for the Cohort 2, Cohort 3, or Part B. Such participants will continue to be followed for at least 24 weeks from the first retreatment dose, but their response to the additional doses will not be included for efficacy analyses.

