#### 9.4.2.1.1 Adverse events

Adverse events will be coded using the Medical Dictionary for Regulatory Activities (MedDRA; version in use by the Sponsor at the time of database lock).

Adverse events will be classified into predefined standard categories according to chronological criteria:

- Pre-treatment AEs: AEs that occurred, worsened, or became serious during the pre-treatment period.

- Treatment-emergent AEs: AEs that occurred, worsened, or became serious during the treatment emergent period.
- Post-treatment: AEs that occurred, worsened, or became serious during the post-treatment period.

Treatment-emergent AEs will be assigned to the dose level group actually received.

The following AEs summaries will be generated with number (%) of participants experiencing at least one event by dose level group for the safety population. Multiple occurrences of the same event in the same participant will be counted only once in the tables, using the maximum (worst) grade by treatment phase. Summaries will be provided for all grades combined and for Grade  $\geq 3$  (including Grade 5):

- Overview of TEAEs: number and percentage of participants with any TEAE, any Grade  $\geq 3$  TEAEs, any serious TEAE, any TEAE leading to death, any TEAE leading to permanent intervention discontinuation, any TEAE of special interest (AESI).
- Summary of TEAEs by primary SOC, high level group term, high level term, and preferred term: number and percentage of participants with at least one TEAE.
- Summary of TEAEs by primary SOC and PT: number and percentage of participants with at least one TEAE.
- TEAEs will also be described according to seriousness, maximum intensity (ie, grade), relation to the IMP and action taken.
- Number and percentage of participants experiencing treatment emergent AESI will be presented by AESI category and PT.
- Post-treatment AEs: overview, summary of AEs and serious AEs by primary SOC and PT.

All AEs reported in the study will be listed, sorted by participant and onset date. Participants presenting TEAEs will be listed sorted by primary SOC and PT. Any deaths, serious adverse events of special interest and other significant AEs, any AEs leading to permanent intervention discontinuation, will be listed.

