1.3 DATA HANDLING CONVENTIONS

This section describes the rules and conventions used in the presentation and analysis of data.

The data will be analyzed following the Sanofi guideline for reporting of Phase 1b/2 studies 'Conventions for analyzing and reporting standard Early Development clinical trial data (except Oncology)' (BTD-009094 v4.0). In the statistical appendices and in-text tables, the following treatment labels will be used:

- Isatuximab 140 mg SC Q2W x2
- Isatuximab 280 mg SC Q2W x6
- Isatuximab 560 mg SC Q2W x6

Individuals who do not meet the criteria for participation in this study (screen failure) may be rescreened. Only the data associated with the final re-screen for a participant will be considered for the definition of analysis populations.

As permitted in the protocol, one participant in Cohort 1 who met retreatment criteria and agreed to be retreated, was retreated as part of Cohort 2. The retreatment period will not be included for any analyses other than listings and will be reported separately. Furthermore, only the data associated with the first treatment period will be considered for the definition of analysis populations. For the retreated participant, the treatment-emergent period is defined as the period from the first IMP administration of the considered study period up to the last IMP administration of the considered study period + 30 days or up to the next study period (excluded), whatever occurred first. For the retreated participant, the following treatment label will be used when applicable:

- Isatuximab 280 mg Retreated SC Q2W x6

For parameters with evaluations before administration and in cases of rechecked value(s) for one participant, only the last observation will be used as baseline in descriptive statistics and derivations of other parameter values.

After baseline, only observations planned in the protocol will be used in descriptive statistics.

For clinical laboratory parameters with nonnumeric values, the imputed values used for the descriptive statistics and/or the flags will be determined by considering the following rules:

- If database value is ‘< X’, the value used will be X/2
- If database value is ‘> X’, the value used will be $X + 10^{[-\text{number of digits of the considered parameter in the database}]}$
- If database value is a range (eg, ‘X – Y’), the values used will be $(Y + X)/2$

If not otherwise stated in the statistical section of the protocol:

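### Part A safety tables count events over a planned window ending on Day 45 at 140 mg x2 but Day 101 at 280 and 560 mg x6, which biases comparisons with 140 mg towards fewer events at that dose

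*Protocol*

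**What the plan says.** Safety by dose level is the primary endpoint of Part A (Protocol 9.4.2.1), and Part A is the only part that was carried out (SAP 1.2).

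- **Window.** The treatment-emergent period "is defined as the period from the first IMP administration up to 30 days after the last IMP administration" (Protocol 9.4.2.1).
- **Regimens.** The first three participants "will receive the D1 and D15 doses only" (Protocol 1.3, note e). The six-dose regimen runs to Day 71 (Protocol 4.1). The reporting groups in SAP 1.3 are "Isatuximab 140 mg SC Q2W x2", "Isatuximab 280 mg SC Q2W x6" and "Isatuximab 560 mg SC Q2W x6".
- **Summary measure.** The AE tables show "number (%) of participants experiencing at least one event by dose level group for the safety population" (Protocol 9.4.2.1.1), and repeats of an event in one participant count once. Laboratory and vital-sign PCSA counts use the same window (Protocol 9.4.2.1.2 and 9.4.2.1.3).
- **SAP changes.** SAP 1.2.2 drops the post-treatment AE summary and adds a detailed listing of all AEs. SAP 1.2.3 adds laboratory and vital-sign listings and drops the out-of-range laboratory summary and the vital-sign descriptive statistics.

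Neither document plans a table over a common window, a rate per unit of exposure, or a column for time at risk.

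**The concern.** The chance that a participant has at least one event grows with the time observed. Here the length of observation is tied to the dose group: the lowest dose has fewer than half as many days in which an event can be tabulated. An event on Day 60 enters the table at 280 or 560 mg. The same event on the same day at 140 mg falls outside the window and, with the post-treatment summary removed, appears only in a listing.

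The comparison at stake is 140 mg against the two six-dose groups. A lower percentage at 140 mg could be read as better tolerability of that dose when part or all of it comes from the shorter window.

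**Working it through.** **1. Dosing days.** Dosing is every 2 weeks, so dose k falls on Day 1 + 14(k − 1): Days 1, 15, 29, 43, 57 and 71. This reproduces the protocol's Day 71 for the sixth dose. As a cross-check, 169 − 71 = 98 days = 14 weeks, the period of assessment after the last dose given in Protocol Table 1.

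**2. Windows.** Last dose day plus 30:
- 140 mg x2: 15 + 30 = Day 45
- 280 mg x6 and 560 mg x6: 71 + 30 = Day 101

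Ratio: 101/45 = 2.24 (2.27 in elapsed days, 100/44). These are planned values; visit windows and early discontinuation can change them. For the one retreated Cohort 1 participant, SAP 1.3 ends the first window at the next study period if that comes sooner, which can only shorten the 140 mg side.

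**3. Effect of window length alone.** The documents give no event rate, so the 45-day risk p is an assumption, varied below.
- *Equal constant hazard in all groups:* risk over 101 days = 1 − (1 − p)^(101/45).
- *Half of the 45-day hazard belongs only to the first two injections:* the exponent is 0.5 + 0.5 × 101/45 = 1.62.
- *All of the hazard belongs to the first two injections:* both windows cover it, so the risk stays at p.

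| 45-day risk | 101 days, constant hazard | Gap (points) | 101 days, half early | 101 days, all early |
|---|---|---|---|---|
| 10% | 21.1% | 11.1 | 15.7% | 10% |
| 30% | 55.1% | 25.1 | 43.9% | 30% |
| 50% | 78.9% | 28.9 | 67.5% | 50% |

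The gap narrows when almost everyone has an event: at a 45-day risk of 90% it is 9.4 points.

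**4. What 3 per group would show.** Exact binomial comparison of one six-dose group with the 140 mg group, constant equal hazard, no dose effect:

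| 45-day risk | x6 group higher | Tie | x6 group lower |
|---|---|---|---|
| 10% | 40% | 46% | 14% |
| 30% | 60% | 26% | 14% |
| 50% | 64% | 25% | 11% |

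**5. 280 against 560 mg.** Both windows end on Day 101, so the ratio is 1 and the expected gap from window length is 0.

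**6. Candidate common windows.** From Day 1 to just before the Day 29 injection, every group has 28 days and two injections (Days 1 and 15). From Day 1 to Day 45, time is equal, but the six-dose groups have had four injections (Days 1, 15, 29 and 43) against two. Under an equal constant hazard the expected gap is 0 in either window.

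**The case against.** The case for leaving the plan alone has real substance.

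- **Much is visible already.** The column labels show x2 and x6, the safety evaluation includes review of individual values, and with at most 9 participants in Part A the timing of events can be read from the listings. This stands, but a listing does not correct the summary tables, which are what will be cited for the primary endpoint.
- **The constant hazard does not fit the best-known reaction.** In the earlier myeloma studies most infusion reactions came with the first infusion, and none came after the second at doses below 10 mg/kg (Protocol 2.3.1). For such events there is little or no bias. This stands and limits the size, not the direction for other events.
- **The analysis is descriptive.** No test is planned (Protocol 9.1), percentages in groups of 3 move in steps of 33 points, and the dose limits between cohorts follow DLT counts and committee review (Protocol 10.1.5 and 10.1.9). This stands. A reader might infer that the tables lead to a wrong dose decision or a false statistical conclusion; the documents do not support that.
- **A Day 45 cut is not like for like.** It compares two injections with four. This is right, and it is why a cut before the Day 29 injection is the better main common window.
- **Ending the window a fixed time after the last dose is a conventional choice.** It is, and the planned tables can stay. The difficulty is in comparing groups whose planned windows differ about twofold.

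**Conclusion.** The point holds for one contrast. Planned windows of 45 and 101 days bias the crude TEAE and PCSA percentages towards fewer events at 140 mg x2 than in either six-dose group. On an equal constant hazard, 45-day risks of 10, 30 and 50% become 21, 55 and 79%. If half of the 45-day hazard sits with the first two injections they become 16, 44 and 68%. For events confined to those injections there is little or no bias.

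A reader might go further and expect a false toxicity gradient across all three doses. The documents do not support that, because 280 and 560 mg have the same window. Nor is a higher percentage at the six-dose regimens certain when dose has no effect: with 3 per group it is a tendency, and ties are common. The consequence is a table that can mislead about the relative tolerability of 140 mg, made harder to notice by the loss of the post-treatment AE summary.

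**What to change.** In SAP 1.2.2 and 1.2.3:

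1. Keep the planned tables, and print participant-days at risk per group for the full window.
2. Add the TEAE overview, TEAEs by SOC and PT, and PCSA counts for a common window in all three groups: Day 1 up to just before the third (Day 29) injection, with the matching cut on Day 29 for the 140 mg group. Observation time and number of injections are then both equal.
3. Optionally repeat these tables for Day 1 to Day 45, labelled as two versus four injections.
4. Base any statement comparing 140 mg with the six-dose groups on the common-window tables, and state that dose and number of injections remain confounded by design after Day 29.

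No new data are needed: AEs are collected throughout the study (Protocol 8.3.1) and all participants are followed for at least 24 weeks (Protocol 4.1). The cost is SAP wording, a date cut in existing table programs, and a few extra tables with 3 planned participants per group. The common window leaves out later events in the six-dose groups; these remain in the full-window tables.
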